### 8.3.2 DEFINITION OF SERIOUS ADVERSE EVENTS

An adverse event is serious when the patient outcome is death, life-threatening, hospitalization, disability, or other serious and important medical events.

### 8.3.3 CLASSIFICATION OF AN ADVERSE EVENT

#### 8.3.3.1 SEVERITY OF EVENT

We will follow the Federal Guidance on this issue.

For adverse events (AEs) not included in the protocol defined grading system, the following guidelines will be used to describe severity.

- **Mild** – Events require minimal or no treatment and do not interfere with the participant's daily activities.
- **Moderate** – Events result in a low level of inconvenience or concern. Moderate events may cause some interference with functioning.
- **Severe** – Events interrupt a participant's usual daily activity and may require systemic intervention. Severe events are usually potentially life-threatening or incapacitating.

#### 8.3.3.2 RELATIONSHIP TO STUDY INTERVENTION/EXPERIMENTAL MANIPULATION

All adverse events (AEs) will have their relationship to study procedures, including the intervention, assessed by an appropriately-trained interventionist and discussion in team meetings. The degree of certainty about causality will be graded using the categories below.

- **Related** – The AE is known to occur with the study procedures, there is a reasonable possibility that the study procedures caused the AE, or there is a temporal relationship between the study procedures and the event. Reasonable possibility means that there is evidence to suggest a causal relationship between the study procedures and the AE.
- **Not Related** – There is not a reasonable possibility that the study procedures caused the event, there is no temporal relationship between the study procedures and event onset, or an alternate etiology has been established.

Our diverse team of psychologist and infectious disease and internal medicine physicians is sufficient to determine the relationship of the AE to the intervention activities.

#### 8.3.3.3 EXPECTEDNESS

The PI along with his senior mentor have the appropriate expertise in depression and HIV care research to be responsible for determining whether an AE is expected or unexpected. An AE will be considered unexpected if the nature, severity, or frequency of the event is not consistent with the risk information previously described for the study procedures. In this behavioral intervention, we expect no serious AEs.

#### 8.3.4 TIME PERIOD AND FREQUENCY FOR EVENT ASSESSMENT AND FOLLOW-UP

The occurrence of an AE or serious AE (SAE) may come to the attention of study personnel during study visits and interviews of a study participant presenting for medical care, or upon review during team meetings.

All AEs, not otherwise precluded per the protocol, will be captured following the Reporting Requirements Summary Sheet from the UCSF IRB (Attached in the IRB application). Information to be collected includes event description, time of onset, clinician's assessment of severity, relationship to study procedures (assessed only by those with the training and authority to make a diagnosis), and time of resolution/stabilization of the event. All AEs occurring while on study will be documented appropriately regardless of relationship. All AEs will be followed to adequate resolution.

Any medical or psychiatric condition that is present at the time that the participant is screened will be considered as baseline and not reported as an AE. However, if the study participant's condition deteriorates at any time during the study, it will be recorded as an AE.

Changes in the severity of an AE will be documented to allow an assessment of the duration of the event at each level of severity to be performed. Documentation of onset and duration of each episode will be maintained for AEs characterized as intermittent.

The interventionist will record events with start dates occurring any time after informed consent is obtained. At each study visit, the interventionist will inquire about the occurrence of AE/SAEs since the last visit. Events will be followed for outcome information until resolution or stabilization. This is determined during weekly team meetings for AEs, and immediate scheduling of meetings for SAEs.

**ALL SAFETY PLANS HAVE BEEN APPROVED BY THE NIMH.****8.3.5 ADVERSE EVENT REPORTING**

The Reporting Requirements outlined by the UCSF Office of Ethics and Compliance will guide all reporting. The principal and co-investigators on this project will report any adverse events to the UCSF IRB within 5 working days should they be deemed related to the study AND are considered serious (defined above) or unexpected (i.e., an adverse event that exceeds the nature, severity or frequency described in the current IRB Application including the protocol and consent form)

**8.3.6 SERIOUS ADVERSE EVENT REPORTING**

The principal and co-investigators on this project will report to the UCSF IRB of any adverse events within 5 working days should they be deemed related to the study AND are considered serious (defined above) or unexpected (i.e., an adverse event that exceeds the nature, severity or frequency described in the current IRB Application including the protocol and consent form)

**8.3.7 REPORTING EVENTS TO PARTICIPANTS**

Any adverse event reported to the UCSF IRB will only be reported to the participant if it is deemed related to the study AND severe, as this is outside the scope of the risks that were discussed in the consent form, but also that the likelihood of a serious adverse event is extremely rare. Our Data and Safety Monitoring Plan approved by the NIMH also includes the ability to schedule an immediate meeting of the PI, the senior faculty mentor, and internal medical monitor.

**8.3.8 EVENTS OF SPECIAL INTEREST**

N/A

**8.3.9 REPORTING OF PREGNANCY**

N/A

**8.4 UNANTICIPATED PROBLEMS****8.4.1 DEFINITION OF UNANTICIPATED PROBLEMS**

This protocol uses the definition of Unanticipated Problems as defined by the Office for Human Research Protections (OHRP). OHRP considers unanticipated problems involving risks to participants or others to include, in general, any incident, experience, or outcome that meets all of the following criteria:

- Unexpected in terms of nature, severity, or frequency given (a) the research procedures that are described in the protocol-related documents, such as the UCSF IRB approved research protocol

and informed consent document; and (b) the characteristics of the participant population being studied;

- Related or possibly related to participation in the research (“possibly related” means there is a reasonable possibility that the incident, experience, or outcome may have been caused by the procedures involved in the research); and
- Suggests that the research places participants or others at a greater risk of harm (including physical, psychological, economic, or social harm) than was previously known or recognized.]

---

#### 8.4.2 UNANTICIPATED PROBLEMS REPORTING

[name] will report unanticipated problems (UPs) to the UCSF IRB. The UP report will include the following information:

- Protocol identifying information: protocol title and number, PI’s name, and the IRB project number.
- A detailed description of the event, incident, experience, or outcome.
- An explanation of the basis for determining that the event, incident, experience, or outcome represents an UP.
- A description of any changes to the protocol or other corrective actions that have been taken or are proposed in response to the UP.

To satisfy the requirement for prompt reporting, UPs will be reported using the following timeline:

- UPs that are serious adverse events (SAEs) will be reported to the IRB immediately and no later than 48 hours after the discovery was made that a UP occurred.
- Any other UP will be reported to the IRB and to the DCC/study sponsor/funding agency within 5 working days of the [name] becoming aware of the problem .
- All UPs should be reported to appropriate institutional officials (UCSF IRB), the NIMH Program Officer, within five days of [name] becoming aware of the problem.

---

#### 8.4.3 REPORTING UNANTICIPATED PROBLEMS TO PARTICIPANTS

Unless the risk/benefit ratio changes or there are risks to breaches of confidentiality for the participant, no UP will be reported to them. If an UP is deemed to directly affect a participant, they will be notified that a meeting is needed to discuss how the issue will be resolved after discussion with the PI, primary mentor, and the UCSF IRB.

## 9 STATISTICAL CONSIDERATIONS

### 9.1 STATISTICAL HYPOTHESES

There are no statistical hypotheses as this is an evaluation of feasibility and acceptability.

### 9.2 SAMPLE SIZE DETERMINATION

Daniel Almirall is a leading expert in SMART designs and developed a sample size estimation tool specifically for pilot SMARTs. First, we propose six treatment sequences and a minimum of four participants to receive them (called “outcome groups” in Figure 1). Second, one must estimate from the literature the percentage of participants who will not show a clinically meaningful response (i.e., “non-response rate”) to a treatment they will be initially randomized to. We used data from a non-inferiority trial of cognitive therapy versus a behavioral activation therapy in general population sample. This trial used clinician-administered diagnostic tools, self-report ratings, fidelity monitoring, and had all interventions delivered by psychologists and social workers. Under these rigorous conditions, 50-60% of participants with mild depression at baseline (range based on self-report and clinician ratings) did not achieve a 50% reduction in depressive symptoms at a 4-month follow-up. Similar results were found for participants with a higher severity of depression at baseline. This estimation tool yielded a total sample size of 45 participants if we observe a non-response rate of 50-60%, a fixed probability of 80% (suggested by Almirall), a minimum of four participants per “outcome group,” and a 10% attrition rate.

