## 1 PROTOCOL SUMMARY

### 1.1 SYNOPSIS

Title:	Feasibility and acceptability of an adaptive treatment intervention for depression and engagement in HIV Care among Latinos living with HIV
Grant Number:	K01MH113475
Study Description:	This is the evaluation of the feasibility and acceptability of an adaptive intervention for depression and engagement in HIV care among Latinos living with HIV. The adaptive intervention is the sequencing of two low-risk behavioral interventions with text-messaging support. The focus of the study is on the sequencing of the interventions.
Objectives *:	Primary Objective: Feasibility of the intervention (i.e., execution of enrollment and intervention session completion rates). Secondary Objectives: Acceptability of the intervention (i.e., evaluation of engagement with intervention). Full details listed in the protocol.
Endpoints *:	Primary Endpoint: Half-way through active engagement with intervention (4 of 8 sessions completed) - this is the follow-up period dictating the sequencing decision. Secondary Endpoints: 12 weeks after enrollment - this is the final follow-up period.
Study Population:	A total of 45 Latino(a)/ Hispanic adult patients (18 or older) that are English or Spanish speaking, are living with HIV, report a mild level of depressive symptoms, and receive care at San Francisco General Hospital Ward 86.
Phase or Stage:	Not applicable
Description of Sites/Facilities Enrolling Participants:	Participants are recruited from Ward 86, at Zuckerberg San Francisco General Hospital in San Francisco, CA. This is a clinic setting with exam rooms, waiting room, and office space. Mission Hall is a research building at the Mission Bay Campus at U.C. San Francisco and includes private office and research study space.
Description of Study Intervention/Experimental Manipulation:	The interventions are behavioral activation therapy (BAT), cognitive-behavioral therapy (CBT) and text-messaging support. BAT is a 8-session one-on-one, in-person or video conferencing, intervention. CBT is an 11-session, one-on-one, in-person or video conferencing, intervention. Text-messaging support are one- and two-way SMS messages.
Study Duration *:	We expect a total of 12-months are needed to enroll 45 participants.
Participant Duration:	Participants are expected to be followed for 3 months.

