### 1.2 SCHEMA

***Flow Diagram - See Attached Figure of Sequential Multiple Assignment Randomized Trial Design.***

## 1.3 SCHEDULE OF ACTIVITIES

	Pre-screening (Pre-consent)	Visit 1 Day 1	Visit 2 Day 7	Visit 3 Day 14 ±7	Visit 4 Day 21 ±7	Visit 5 Day 28 ±7	Visit 6 Day 35 ±7	Visit 7 Day 42 ±7	Visit 8 Day 49 ±7	Visit 9 Day 56 ±7	Visit 10 Day 63 ±7	Visit 11 Day 70 ±7	Final Visit Day 84 ±7
Screen for Eligibility	X												
Informed Consent		X											
Demographics		X											
Depression and Text-Message Criteria		X					X						
Outcome Evaluation													
Depression Ratings		X	X	X	X	X	X	X	X	X	X	X	X
Randomization		X		X									
1 st Stage Intervention		X	X	X	**	X*	X* 						
Primary Tailoring Variable - Decision Point on Sequencing				X									
2 nd Stage Intervention					X	X	X*	X*	X*	X*	X*	X*	
Adverse Events Reporting			X	X	X	X	X	X	X	X	X	X	X

\*Participants will all start with the first stage treatment - This is BAT with or without text-messaging support. After 3 of 5 sessions - approximately half-way through the intervention - their depression ratings are assessed that specifically inform the next course - This is called the second-stage treatment. Participants may either continue to complete the 5 sessions their first-stage treatment (i.e., BAT), get one extra booster session (denoted by \*1), or switch to CBT, which includes up to 11 sessions (denoted by \*).

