## 8 STUDY ASSESSMENTS AND PROCEDURES

### 8.1 ENDPOINT AND OTHER NON-SAFETY ASSESSMENTS

The focus of this study is on the feasibility of carrying out the assessment of a primary tailoring variable (PTV). A PTV is the cutoff score to decide whether a participant showed a clinically meaningful response to BAT or BAT & mHealth at a 1-month follow-up point. The preliminary cutoff score for the pilot SMART is defined as a decrease in a PHQ-9 score from the "moderate" to "mild" (or below) depression symptom severity category after 4 weeks (or after 4 of 8 sessions of BAT). The rationale for the follow-up period is to identify early who is a "responder" or "non-responder" to a 1st-stage treatment. The "responder/non-responder" decision is used to decide whether, when, and how to adapt a 1st-stage treatment. The follow-up point is the mid-way point of the brief intervention, that is, after 3 of 5 BAT sessions are complete. This cutoff score is supported by a randomized placebo-controlled trial that showed BAT to be associated with reduced depression more per week than a cognitive therapy on a self-rating scale. The same depression rating is done at the final follow-up period at the end of the final intervention session.

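### The rule that triggers re-randomisation is stated in conflicting ways, and the 50-60% non-response rate behind N=45 comes from a different event, so the stated 80% depends on which rule applies

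*Combined protocol and SAP*

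**What the plan says.** Sample size (protocol 9.2). The plan wants at least four participants in each of six treatment sequences. It takes non-response from a general-population trial of cognitive therapy versus behavioural activation, where 50-60% of those with mild baseline depression "did not achieve a 50% reduction in depressive symptoms at a 4-month follow-up", and reports similar results at higher severity. It concludes: "This estimation tool yielded a total sample size of 45 participants if we observe a non-response rate of 50-60%, a fixed probability of 80" per cent, with 10% attrition. The SAP has no sample-size text.

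The response rule is described in several places:

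| Feature | Version | Where |
|---|---|---|
| Timing | Day 14 ±7, the column marked for "Primary Tailoring Variable - Decision Point on Sequencing" | 1.3 |
| | 4 weeks | 8.1 |
| Sessions completed | 3 of 5: "The follow-up point is the mid-way point of the brief intervention, that is, after 3 of 5 BAT sessions are complete" | 8.1; also 1.3, 6.1.1 |
| | 4 of 8: "Half-way through active engagement with intervention (4 of 8 sessions completed") | 1.1; also 6.1.2, 8.1 |
| Criterion for response | PHQ-9 falls from moderate to mild or below (called preliminary) | 8.1 |
| | any improvement, since non-response is no change or worse | 6.1.2 |
| | a PHQ-9 cut-off score | 6.1.1, 6.1.2 |

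On entry severity, 5.1 admits from mild upward, 1.1 describes people who "report a mild level of depressive symptoms", and 6.5 speaks of mild to moderate depression.

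**The concern.** The non-response rate decides how many participants reach each of the six groups. If it is low, the four second-stage groups run short. If it is high, the two responder groups do. The 80% is the only quantitative basis given for N, and it rests on a rate for a different outcome at a later time point: 4 months, against a participant follow-up of 3 months.

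The trial's own rule cannot yet be given a rate, because it is not one rule. The treatment of people who enter below moderate matters most. Read literally, section 8.1 can never class them as responders, since they cannot move from moderate to mild. Under a cut-off reading they may count as responders without changing at all. The two readings push the rate in opposite directions.

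Section 9.4.1 makes 80% retention in all outcome groups a primary feasibility outcome, so very small or empty groups would make one of the main results hard to interpret.

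**Working it through.** **Inputs.** From 9.2: N=45, six groups, at least 4 in each, non-response q = 50-60%, 80% probability, 10% attrition. Assumed, because the text does not state them: 1:1 first stage, the same q in both arms, an even second-stage split. The estimation tool's method is not in the documents.

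**Formula.** In an arm of n, non-responders X ~ Bin(n, q). Two second-stage groups of at least 4 need X ≥ 8. A responder group of at least 4 needs X ≤ n − 4. The joint probability is the product over the two arms of P(8 ≤ X ≤ n − 4).

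**Reproducing 45.** The smallest N reaching 0.80 is 42, 38 and 36 at q = 0.50, 0.55 and 0.60. Dividing by 0.9 gives 46.7, 42.2 and 40, so 47, 43 and 40 enrolled. The stated 45 fits these inputs to within about two participants at 50% and 55%, and is generous at 60%.

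**Sensitivity to the rate.** 45 × 0.9 = 40.5, so the columns are 40 counted (20/20, the full 10% lost before groups are counted) and 45 counted (22/23, none lost).

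| Non-response | 40 counted | 45 counted |
|---|---|---|
| 40% | 0.34 | 0.54 |
| 50% | 0.75 | 0.89 |
| 60% | 0.93 | 0.98 |
| 70% | 0.80 | 0.88 |
| 80% | 0.35 | 0.47 |

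As an example, at 50% with 20 per arm, P(8 ≤ X ≤ 16) = 0.867, and 0.867² = 0.75. The probability is at least 0.80 for about 52-70% (40 counted) or 47-73% (45 counted).

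**Effect of the rule.** Let a share f enter below moderate, and let q = 50-60% of the rest not respond. Both are assumptions; the baseline mix is not given. If below-moderate entrants can never respond (8.1 read literally), overall non-response is f + (1 − f)q. If they stay below a cut-off and count as responders, it is (1 − f)q.

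| f | Reading | Overall non-response | 40 counted | 45 counted |
|---|---|---|---|---|
| 20% | 8.1 literal | 60-68% | 0.85-0.93 | 0.92-0.98 |
| 20% | cut-off score | 40-48% | 0.34-0.68 | 0.54-0.84 |
| 50% | 8.1 literal | 75-80% | 0.35-0.60 | 0.47-0.72 |
| 50% | cut-off score | 25-30% | 0.01-0.05 | 0.03-0.13 |

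For f = 20%, for example: 0.2 + 0.8 × 0.5 = 0.60, against 0.8 × 0.5 = 0.40.

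**Timing.** Section 6.1.1 spaces the BAT-alone sessions two weeks apart. Starting on Day 1, the third falls on Day 29 (Days 1, 15, 29). That is outside the Day 14 ±7 window in 1.3.

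**Second-stage allocation.** If each non-responder were allocated by unblocked 1:1 randomisation, 50-60% non-response would give 0.33-0.60 (40 counted) or 0.50-0.76 (45 counted). The calculation therefore needs a near-even split. In simulation, permuted blocks of 2 and 4 within first-stage arm give about 0.73 at 50% with 40 counted. Adding English/Spanish strata (assumed 50/50 or 30/70) lowers this to about 0.66-0.67.

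**The case against.** Section 9.2 is open about its source. It names the outcome and the time point, and makes N conditional on observing 50-60%. That stands, so nothing is concealed. A stated condition is still not evidence that it will hold under this trial's rule, and the remark about similar results at higher severity concerns the same 50%-reduction outcome in the source trial.

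A pilot is also meant to learn this rate. Section 8.1 calls the cut-off preliminary, and section 4.2 says the results will inform a full-scale trial. Not knowing the rate is therefore no fault. But participants have to be classified during the pilot, so the rule itself must be settled.

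The consequence is small. Section 9.1 states no hypotheses, analyses are descriptive, and 80% or better holds over most of the plan's own 50-60% range. The link to the retention outcome should not be pressed either: in a group of exactly four, one loss gives 75%, so that outcome is fragile even when the sizing target is met.

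A reader might infer that 45 is miscalculated or too small. The documents support neither. The figure approximately reproduces, and the rate under the PHQ-9 rule is unknown and could lie on either side of 50-60%. Nor do the f scenarios predict failure: at f = 20%, one reading meets 80% and the other mostly does not.

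**Conclusion.** The concern holds as an inconsistency in the re-randomisation rule, with an unsupported 80% as its consequence. The conflicts in timing, session count and criterion can be read directly from the protocol, as can the mismatch between the 4-month, 50%-reduction rate and every version of the rule. Confidence in these is high.

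The probabilities are conditional. They rest on 1:1 arms, equal rates, an even second-stage split and an assumption about when attrition occurs; the f scenarios also assume a baseline mix. They show that the choice of rule can move the chance of filling all six groups from above 0.90 to below 0.10. They do not show where this trial lies. The text of 6.3 describes randomisation before the intervention starts and does not say how the second stage is allocated. The SMART figure was not available here and may do so. The point should be addressed, but it does not call for a change in N.

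**What to change.** Keep N=45.

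1. Reconcile the response rule and its timing across 1.1, 1.3, 6.1.1, 6.1.2 and 8.1, including session spacing and how participants entering below moderate are classified. Which rule to adopt is for the investigators; none is proposed here.
2. In 9.2, state that 50-60% is a proxy from a different outcome and time point. Replace the single 80% with a short table over, for example, 40-80% non-response, with and without 10% attrition. List the assumptions and the overall non-response expected under the reconciled rule.
3. Secondary: if the SMART figure or randomisation list does not already give near-even second-stage allocation, state in 6.3 that it is blocked within first-stage arm, and whether the English/Spanish stratification is kept. If the figure or list does provide it, a cross-reference is enough.

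The cost is protocol wording, one small table and possibly a second-stage list, with no extra participants. The downside is a less favourable stated probability in part of the range, and a somewhat lower one if language strata are kept.

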### 9.3 POPULATIONS FOR ANALYSES

The same will consist of Latinos living with HIV, no sub-analyses are planned regarding the evaluation of feasibility and acceptability.

